The primary analysis uses the stratified log rank test to compare treatment group to control group through Day 29 with respect to TTCl. Covariate factors may include country duration of symptoms prior to enrollment, comorbidity and best supportive treatment. Note that if some strata are too small, they might be combined together to allow statistical method work well.

For each group, the Kaplan-Meier estimate of TTCl survival function will be constructed. Hazard ratio of SCTA01 vs. placebo with two-sided 95% CI will be derived from the stratified Cox proportional hazard model. The number of patients with a TTCl event and number of patients censored for the TTCl analysis will be summarized by treatment group. Percentage of subjects in each category using the 8-point ordinal scale up to Day 29 will also be summarized by treatment group.

PK Analysis

Population pharmacokinetic analysis will be performed using NONMEM® (Version 7.4, Icon Inc, PA, USA)..

Immunogenicity Analysis

To collect the proportion of subjects with anti-SCTA01 antibody and to evaluate the change of anti-SCTA01 antibody in patient serum.

Non-Response to SCTA01 assessments

Number and proportion of non-responders having mutations in the gene encoding the SARS-CoV-2 Spike protein through Day 29. A non-responder is defined as a patient who does not achieve a reduction in viral shedding or persistence viral presence or have a rebound in viral shedding following suppression (Phase II, III).

Stopping Infusion Criteria: If a severe allergic reactions (including anaphylaxis) (Grade 3 or higher) is observed during infusion, the infusion will be immediately stopped and no further SCTA01/placebo treatment will be administered to the subject.

TABLE OF CONTENTS

PROTOCOL SYNOPSIS.....	2
TABLE OF CONTENTS	10
LIST OF TABLES	14
LIST OF FIGURES	15
SCHEMA.....	16
ABBREVIATIONS AND DEFINITIONS OF TERMS.....	17
1. STUDY OBJECTIVES AND ENDPOINTS	19
1.1. Primary Objectives	19
1.2. Secondary Objectives	19
1.3. Exploratory Objectives.....	19
1.4. Primary Endpoints.....	19
1.5. Secondary Endpoints.....	19
1.6. Exploratory Endpoints.....	21
2. BACKGROUND	22
2.1. Spike Protein and SARS-CoV-2	22
2.2. Convalescent Plasma in the Treatment of COVID-19	22
2.3. Potential Efficacy	22
2.4. Booster Neutralizing Antibodies against COVID-19.....	23
2.5. SCTA01 is a Neutralizing Antibody against SARS-CoV-2.....	23
2.6. Preclinical Pharmacokinetics	23
2.7. Preclinical Pharmacodynamics	24
2.8. Preclinical Toxicology	26

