3.5. Dose Modification

No dose modification is needed.

All subjects should be monitored closely for infusion-related reactions and anaphylaxis for at least 2 hours after the completion of the infusion. Emergency equipment and medication for the treatment of infusion-related reactions and anaphylaxis must be available for immediate use during the infusion and the post-infusion monitoring period if required for treatment.

Sites should have appropriately trained medical staff to recognize and treat infusion-related reaction and anaphylaxis. It is recommended that participants who experience an infusion-related reaction or anaphylaxis can be treated per the local standard of care.

The infusion can be reduced to 50% of the infusion rate / interrupted then be restarted at 50% of the original rate if any of the following adverse events are observed:

- Sustained/severe cough
- Rigors/chills
- Rash, pruritus (itching)
- Urticaria (hives, welts, wheals)
- Diaphoresis (sweating)
- Hypotension
- Dyspnea (shortness of breath)
- Vomiting
- Flushing

If investigators feel there is a medical need for treatment or discontinuation of the infusion other than described above, they should use clinical judgment to provide the appropriate response according to standard clinical practice.

The infusion should be terminated and not restarted if any of the following adverse events occur:

- Anaphylaxis*
- Laryngeal/pharyngeal edema
- Severe bronchospasm
- Seizure
- Severe hypotension
- Other neurological symptoms (confusion, loss of consciousness, paresthesia, paralysis, etc)
- Any other symptom or sign that, in the opinion of the investigator, warrants termination of the

intravenous infusion

*Consider anaphylaxis if the following is observed ²⁷: acute onset of an illness (minutes to several hours) with involvement of the skin, mucosal tissue, or both (eg, generalized hives, pruritus or flushing, swollen lips-tongue-uvula) and **at least one of the following**:

- Respiratory compromise (eg, dyspnea, wheeze-bronchospasm, stridor, reduced peak expiratory flow, hypoxemia)
- Reduced blood pressure or associated symptoms of end-organ dysfunction (eg, hypotonia [collapse], syncope, incontinence).

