6. STUDY INTERVENTION DISCONTINUATION

6.1. Individual Infusion Halting

In rare instances, it may be necessary for a subject to permanently discontinue study intervention. If study intervention is definitively discontinued, the participant will remain in the study for follow-up.

For an individual subject, the infusion must be terminated and not restarted if severe infusion-related reaction(s) mentioned in Section 3.5 occur.

The treatment for any given subject may be stopped for SUSARs related to SCTA01, clinically significant adverse reactions, severe laboratory abnormalities, or any other medical conditions that indicate to the investigator that continued dosing is not in the best interest of the patient.

In addition, a subject in this clinical study may discontinue study drug at their requests for any reason. After the discontinuation, every effort should be made to encourage the subject to remain in the study for the duration of their planned outcome assessments.

The reason for subject discontinuation of study drug should be documented in the case report form.

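### Section 3.5 does not carry over the Synopsis rule that an allergic reaction of Grade 3 or higher ends the infusion for good, and for generalized urticaria it permits a restart

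*Combined protocol and SAP*

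**What the plan says.** Four places bear on when an infusion must end.

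- **Synopsis, Stopping Infusion Criteria.** The rule is mandatory and graded: "If a severe allergic reactions (including anaphylaxis) (Grade 3 or higher) is observed during infusion, the infusion will be immediately stopped". The same sentence bars giving that patient any more study drug or placebo. Anaphylaxis is included in the trigger but is not required for it.
- **Section 3.5, Dose Modification.** There are two lists. The first is permissive: "The infusion can be reduced to 50% of the infusion rate / interrupted then be restarted at 50% of the original rate". It includes the entry "Urticaria (hives, welts, wheals" without any limit on grade or extent, and also dyspnea and "Sustained/severe cough". The second is directive: "The infusion should be terminated and not restarted if any of the following adverse events occur". It names anaphylaxis, edema of the larynx or pharynx, severe bronchospasm, seizure, severe hypotension, neurological symptoms, and anything else the investigator judges to warrant termination. A footnote defines anaphylaxis as skin or mucosal involvement (its examples are "generalized hives, pruritus or flushing, swollen lips-tongue-uvula") together with respiratory compromise or reduced blood pressure and its consequences.
- **Section 6.1, Individual Infusion Halting.** "the infusion must be terminated and not restarted if severe infusion-related reaction(s) mentioned in Section 3.5 occur". A separate sentence allows, but does not require, stopping for other significant reactions.
- **Section 8.2.7, Table 6.** This grades acute allergic reactions. Localized urticaria is Grade 1 or 2. Grade 3, labeled severe, is any one of generalized urticaria, angioedema needing intervention, or mild bronchospasm. Grade 4 covers acute anaphylaxis, life-threatening bronchospasm and laryngeal edema.

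**The concern.** The Synopsis sets its threshold at Grade 3. The no-restart list in Section 3.5 is a list of named events with no grade, and it does not mention Grade 3 allergic reactions. Section 6.1 sends the reader to Section 3.5, so a site managing a reaction would naturally work from that section.

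Two things are at stake. The first is patient safety: a patient could be re-exposed after a reaction for which the Synopsis requires a permanent stop. The protocol treats the same reaction as an adverse event of special interest, reportable within 24 hours. The second is consistency between sites: the same reaction could end the infusion at one site and lead only to a slower rate or a pause at another. It would then be handled differently in the summary of adverse events leading to study drug discontinuation (Section 9.6).

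**Working it through.** No arithmetic applies. The check follows individual reactions through each rule. In the first four rows the signs that would make the event anaphylaxis under the Section 3.5 footnote are assumed absent.

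| Reaction during infusion | Table 6 | Synopsis | Section 3.5 |
|---|---|---|---|
| Localized urticaria | Grade 1 or 2 | Not triggered | Slowing or restart permitted; no conflict |
| Generalized urticaria | Grade 3 | Permanent stop | Slowing or restart expressly permitted; not on the no-restart list |
| Mild bronchospasm | Grade 3 | Permanent stop | No-restart list names only severe bronchospasm; if it presents as dyspnea, slowing or restart is permitted |
| Angioedema needing intervention, outside larynx and pharynx | Grade 3 | Permanent stop | On neither list |
| Anaphylaxis, life-threatening bronchospasm, laryngeal edema | Grade 4 | Permanent stop | Covered by the no-restart list; no conflict |

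1. **What the Synopsis rule means here.** Treatment is one infusion of a single dose (Sections 3.3 and 5.2). A ban on further treatment can therefore only refer to the rest of that infusion, so it cannot be read as allowing a pause and restart.

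2. **Where the two sections part.** For allergic reactions, the Section 3.5 no-restart list covers Grade 4 of Table 6 but not Grade 3. That is the source of the mismatch.

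3. **How far the anaphylaxis entry helps.** Generalized hives or swelling of the lips or tongue move to the no-restart list once a respiratory or blood-pressure sign is also present. Generalized hives alone do not qualify. Neither does mild bronchospasm without skin or mucosal involvement, nor angioedema without respiratory or circulatory signs.

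4. **Express conflict versus gap.** For generalized urticaria one section forbids what the other permits by name. For mild bronchospasm the permission arises only through the symptom, dyspnea. For angioedema outside the larynx and pharynx there is no restart permission, only an omission from the list that requires a stop.

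5. **Section 6.1.** It can be read in two ways. On one, any reaction mentioned in Section 3.5 ends the infusion once it is severe; since Table 6 labels Grade 3 severe, severe urticaria must stop. On the other, it simply points to the no-restart list, and urticaria is not on it. No grade is given to decide between them. The word severe does not by itself select the no-restart list, because "Sustained/severe cough" is on the restartable one.

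**The case against.** The strongest reply is that Section 6.1 already resolves this. Urticaria is mentioned in Section 3.5, Table 6 calls its generalized form severe, and Section 6.1 says severe reactions mentioned in Section 3.5 must end the infusion. That is a natural reading, and it agrees with the Synopsis. The cough entry is a limited counterexample, since cough is not in the allergic row of Table 6. What stands is that Section 6.1 softens the conflict for urticaria and dyspnea. It does not remove it, because the other reading is also open and no grade is stated. It gives less help with angioedema outside the larynx and pharynx, which neither list in Section 3.5 names as an event; lip and tongue swelling appears only as an example in the anaphylaxis footnote.

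A second reply is that the rules can be followed together: Section 3.5 only permits a restart, and an investigator who stops complies with every section. That is correct, and it is why the point is minor. A reader might infer that Section 3.5 instructs sites to restart, or that no site could comply with both texts. The permissive wording does not support either. A reader might also infer that the whole slow-or-restart list contradicts the Synopsis. It does not: entries such as rigors, vomiting and sweating are not in the allergic row of Table 6, and for a Grade 2 cytokine release reaction Table 6 itself contemplates interruption.

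A third reply is that safeguards exist: vital signs every 15 minutes in the first hour and every 30 minutes to the end of infusion, emergency equipment, trained staff, and mandatory termination for anaphylaxis. These limit harm, but they do not tell a site whether a Grade 3 reaction allows a restart.

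**Conclusion.** The inconsistency is real and worth correcting, but minor. The Synopsis requires a permanent stop at Grade 3; the Section 3.5 no-restart list does not include Grade 3 acute allergic reactions as Table 6 defines them; and Section 6.1 does not clearly close the difference. It is express for generalized urticaria without anaphylaxis signs, and it also arises for mild bronchospasm and for angioedema needing intervention outside the larynx and pharynx.

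The conclusion assumes that the grade in the Synopsis is the Table 6 grade. The Synopsis does not cite that table, but Section 8.2.7 makes it the protocol's grading for acute allergic reactions.

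The documents give no rate for any of these reactions, so the number of patients affected cannot be estimated. Nothing here supports inferring a statistical consequence for the trial's main result: no input to alpha, power or the primary analysis depends on this rule.

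**What to change.** In Section 3.5:

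1. Add to the terminate-and-do-not-restart list: any acute allergic reaction of Grade 3 or higher (Table 6).
2. State that this list takes precedence over the slow-or-restart list.
3. Limit the urticaria entry on the slow-or-restart list to Grades 1 and 2.

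In Section 6.1, cite the same Grade 3 criterion and Table 6.

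The first two changes also cover mild bronchospasm presenting as dyspnea and angioedema outside the larynx and pharynx, without rewriting other entries. The third removes the one express contradiction. Interruption stays available for non-allergic reactions, including a Grade 2 cytokine release reaction.

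The cost is a wording amendment, with written IRB/IEC approval before use (Section 10.5), and possibly a few more incomplete infusions at sites not already following the Synopsis rule. The documents give no basis for estimating how many.

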C _{max}	Maximum Concentration
CCP	COVID-19 Convalescent Plasma
CL	Clearance
CrCL	Creatinine Clearance
COVID-19	Coronavirus Disease 2019
CRF	Case Report Form
CRO	Contract Research Organization
CSR	Clinical Study Report
CT	Computed Tomography
DAIDS	Division of AIDS
DLT	Dose Limited Toxicity
EC	Ethics Committee
ECG	Electrocardiogram
ECMO	Extracorporeal Membrane Oxygenation
EDC	Electronic Data Collection
eGFR	Estimated Glomerular Filtration Rate
EOS	End of Study
EUA	Emergency Use Authorization
FDA	Food and Drug Administration
FiO ₂	Fraction of Inspired Oxygen
GCP	Good Clinical Practice
GLP	Good Laboratory Practice
IA	Interim Analysis
ICF	Informed Consent Form
ICH	International Conference on Harmonization

Abbreviation	Definition
ICSR	Individual Case Safety Report
IRB	Institutional Review Board
ICU	Intensive Care Unit
IWRS	Interactive Web Response System
ITT	Intention to Treat
IDMC	Independent Data Monitoring Committee
LDH	Lactate Dehydrogenase
NOAEL	No Observed Adverse Effect Level
NP	Nasopharyngeal
OP	Oropharyngeal
PaO ₂	Arterial Partial Pressure of Oxygen
PT	Preferred Term
PKS	Pharmacokinetics Set
PKCS	PK Concentration Set
PKPS	PK Parameter Set
RBD	Receptor Binding Domain
RR	Rate Ratio
RT-qPCR	Quantitative Reverse Transcription Polymerase Chain Reaction
S	Spike
SAEs	Serious Adverse Events
SARS-CoV-2	Severe Acute Respiratory Syndrome Coronavirus 2
SCr	Serum Creatinine
SCT	Sinocelltech, Ltd.
SID	Subject Identification
SOFA	Sequential Organ Failure Assessment
SOP	Standard Operating Procedures
SUSAR	Suspected Unexpected Serious Adverse Reaction
SpO ₂	Pulse Oxygen Saturation
SS	Safety Set
T _{max}	Time of Maximum Concentration
TTCI	Time to Clinical Improvement
T _{1/2}	Half-life Time
TEAEs	Treatment-emergent Adverse Events
Vd	Apparent Volume of Distribution

1. STUDY OBJECTIVES AND ENDPOINTS

1.1. Primary Objectives

- To evaluate the clinical efficacy of SCTA01 as assessed by time to clinical improvement (Phase II, III).

1.2. Secondary Objectives

- To evaluate the clinical efficacy of SCTA01 as assessed by clinical severity, hospitalization, mortality (Phase II, III);
- To evaluate the safety of SCTA01 (Phase II, III);
- To evaluate the virologic efficacy of SCTA01 (Phase II, III);
- To evaluate the pharmacokinetics of SCTA01 (Phase II);
- To evaluate the immunogenicity of SCTA01 (Phase II, III).

1.3. Exploratory Objectives

- To explore the correlation between the baseline serological antibody level and therapeutic effect (Phase II, III);
- To evaluate the virologic efficacy of SCTA01 as assessed by quantitative SARS-CoV-2 virus in patient's blood (Phase II, III).

1.4. Primary Endpoints

- Time to clinical improvement (TTCI) up to Day 29. TTCI is defined as the time (in days) from randomization to the first day on which a patient satisfies Point 1, 2, or 3 on the 8-point ordinal scale¹ and maintains a score ≤ 3 at least 48 hours (initial improvement) and maintains this up to Day 29 (sustained improvement) (Phase II, III).

1.5. Secondary Endpoints

- Clinical efficacy of SCTA01:
 - Proportion of patients with initial clinical improvement at Day 29 (Phase II, III);
 - Proportion of patients with sustained clinical improvement at Day 29 (Phase II, III);
 - Time to initial clinical improvement up to Day 29 (Phase II, III);
 - Time to discharge from hospital, followed by being alive and home for 14 consecutive days prior to Day 90 (Phase II, III);
 - Proportion of patients discharged from hospital, followed by being alive and home for 14 consecutive days prior to Day 90 (Phase II, III);
 - All-cause mortality up to Day 29, record date and cause of death (if applicable) (Phase II, III);

- Percentage of subjects in each category on the 8-point ordinal scale (time frame: Days 3, 5, 8, 11, 15, 22, and 29) (Phase II, III);
 - Proportion of patients alive and free of respiratory failure up to Day 29 (Phase II, III);
 - Proportion of patients who are discharged from acute care up to Day 29 (Phase II, III);
 - Days of supplemental oxygen (if applicable) up to Day 29 (Phase II, III);
 - Days of non-invasive ventilation/high flow oxygen (if applicable) up to Day 29 (Phase II, III);
 - Days of invasive mechanical ventilation/extracorporeal membrane oxygenation (ECMO) (if applicable) up to Day 29 (Phase II, III);
 - Time to hospital discharge up to Day 29 (Phase II, III);
 - Number and proportion of non-responders having mutations in the gene encoding the SARS-CoV-2 S protein through Day 29. A non-responder is defined as a patient who does not achieve a reduction in viral shedding or persistence viral presence or have a rebound in viral shedding following suppression (Phase II, III).
- Safety of SCTA01:
 - Cumulative incidence of serious adverse events (SAEs) (Phase II, III);
 - Cumulative incidence of Grade 1, 2, 3 and 4 clinical and/or laboratory adverse events (AEs) (Phase II, III);
 - Discontinuation or temporary suspension of infusions (for any reason) (Phase II, III);
 - Chemistries, hematology, urinalysis, coagulation function, IL-6, ferritin, procalcitonin, thrombin time, D-dimer (Phase II, III);
 - Number and proportion of patients who are suspected to experience antibody-dependent enhancement (ADE) (Phase II, III).
- Virologic efficacy of SCTA01:
 - Change from baseline in viral shedding as measured by quantitative reverse transcription polymerase chain reaction (RT-qPCR) in NP or OP swab samples (Phase II, III);
 - Time-weighted average change from baseline in viral shedding as measured by RT-qPCR in NP or OP swab samples (Phase II, III);
 - Time to SARS-CoV-2 RNA negative in NP or OP swab samples as determined by RT-qPCR (Phase II, III).
- Pharmacokinetics (PK) of SCTA01:
 - Pharmacokinetic characteristics in severe COVID-19 patients (Phase II).
- Immunogenicity of SCTA01:

- Immunogenicity assessment include the number and percentage of subjects who develop detectable ADA (Phase II, III).

1.6. Exploratory Endpoints

- The correlation between the baseline serological antibody level and therapeutic effect (Phase II, III);
- Quantitative SARS-CoV-2 virus in patient's blood (Phase II, III).

2. BACKGROUND

2.1. Spike Protein and SARS-CoV-2

The pandemic of SARS-CoV-2 has spread globally, and causing massive death and economic hardship. By 17 Dec 2020, there were 74,226,214 cases confirmed infection and 1,649,032 deaths worldwide, and in the United States, there were 16,979,762 cases confirmed infection, and 307,501 deaths². Although Remdesivir[®] is approved for COVID-19 in the United States³, Itolizumab is approved for COVID-19 in India and Cuba⁴, and FDA issued EUAs for SARS-CoV-2 neutralizing mAbs of Lily's LY-CoV555⁵ and Regeneron's Casirivimab and Imdevimab⁶ for the treatment of mild to moderate COVID-19, but there are still huge unmet clinical needs for treating COVID-19, especially for treating severe and critical COVID-19 patients.

The spike (S) glycoprotein of SARS-CoV-2 is a critical target for diagnosis and treatment. The S protein binds to angiotensin-converting enzyme 2 (ACE2), and helps virus entry into host cells. The SARS-CoV-2 has a 10 ~ 20 fold stronger affinity than SARS-CoVs' binding to ACE2, which account for its high infectivity⁷.

2.2. Convalescent Plasma in the Treatment of COVID-19

The infusion of convalescent plasma is not a novel therapeutic method. It has been evaluated against a variety of viral diseases, which includes severe acute respiratory syndrome (SARS), influenza H1N1 and Ebola, with potential benefits⁸⁻¹⁰. In this COVID-19 epidemic, it has also been tested and made some progress.

2.3. Potential Efficacy

The convalescent plasma therapy showed potential therapeutic effect against COVID-19 in China. There were five critically ill patients with SARS-CoV-2 infection who were transfused with convalescent plasma. Their clinical conditions improved, including normalization of body temperature, decreased Sequential Organ Failure Assessment (SOFA) score, gradually decreasing and ultimately negative viral loads, and increased titers of specific neutralizing antibodies against SARS-CoV-2⁷. Convalescent plasma therapy also showed a beneficial effect in two studies, which consisted of 10 and 6 critical patients, respectively^{12, 13}. All the patients showed relief of clinical symptoms, improved laboratory and pulmonary radiology results to some extent. There were also another 4 cases with severe SARS-CoV-2 infection who were reported to have completely recovered following convalescent plasma infusion¹⁴. The transfusion of convalescent plasma also shows clinical benefit in six patients with critical SARS-CoV-2 infection in Mexico¹⁵. Moreover, in the US, Eric Salazar et al. conducted a clinical trial involving 25 critical patients who received the treatment of convalescent plasma¹⁶. 9 patients (36%) showed clinical improvement when evaluated by a modified World Health Organization 6-point ordinal scale on the 7th day after transfusion. 19 cases (76%) were improved or discharged on the 14th day. No specific adverse events with convalescent plasma treatment were observed. Salazar and colleagues evaluated 136 individuals with COVID-19 who received convalescent plasma and who had data available for 28-day outcomes. These individuals were well-matched to 251 non-transfused control COVID-19 patients. The analysis that these investigators performed indicated that there was a statistically significant reduction in mortality at 28 days that was most notable in the 112 patients transfused within 72 hours of admission with plasma having a high anti-spike protein receptor binding domain

titer of $\geq 1:1350$ ¹⁷. These studies described above indicate that convalescent plasma therapy is well tolerated, beneficial for symptom relief and disease control in COVID-19 patients. So on August 23, 2020, the U.S. Food and Drug Administration (FDA) issued an Emergency Use Authorization (EUA) for COVID-19 Convalescent Plasma for the treatment of hospitalized patients with COVID-19¹⁸. But limitations of these studies include non-randomized, open label, retrospective, etc. So adequate and well-controlled randomized trials remain nonetheless necessary for a definitive demonstration of COVID-19 convalescent plasma (CCP) efficacy and to determine the optimal product attributes and the appropriate patient populations for its use.

